5.2 Protocol deviations

The number and percentage of subjects with an important protocol deviation and with each category of important protocol deviation (as described in [Section 3.4](#)) will be presented by treatment group at completion of AS0008 and overall for the ES.

Important protocol deviations, including deviation type and description, will be listed for the ES.

A separate listing of COVID-19 related important protocol deviations will be presented, based on the ES. COVID-19 related important deviations will be identified by the prefix of 'COVID' in the deviation verbatim text.

6 DEMOGRAPHICS AND OTHER BASELINE CHARACTERISTICS

6.1 Demographics

Demographic variables (age [at time of informed consent], gender, racial group, ethnicity, weight, height, body mass index [BMI], country, and geographic region) will be summarized by treatment group at completion of AS0008 and overall for the SS.

One summary table will be produced for AS0008 Baseline values. Age, sex, weight and BMI collected at AS0009 EV will be listed only.

Age and BMI will be summarized as continuous and as categorical variables:

Age will be categorized as:

- ≤ 18 , $19- < 65$, ≥ 65 years (clinicaltrials.gov requirement).
- $18- < 65$, $65- < 85$, ≥ 85 years (EudraCT requirement).
- $18- < 45$, $\geq 45- < 65$, ≥ 65 years (bimekizumab program conventions).

BMI (kg/m^2) is calculated based on the height (in m) and the weight (in kg) using the formula:

$$\frac{\text{BMI} = \text{weight}}{\text{height}^2} \quad (8)$$

Even if available in the database, BMI will be re-calculated. BMI is rounded to 1 decimal place. BMI will be categorized as follows: < 25 , $25- < 30$, $\geq 30 \text{ kg}/\text{m}^2$.

Demographic data, including AS0008 Baseline and AS0009 EV values for the repeated variables, will be listed for the ES.

6.2 Other baseline characteristics

AS history including the time since first diagnosis of AS (at time of enrolment in AS0008 and at time of enrolment in AS0009), time since first symptoms of AS (at time of enrolment in AS0008 and at time of enrolment in AS0009), age at first diagnosis date, and AS subtype (clinical criterion a, b, c or radiologic criterion) will be summarized by treatment group at completion of AS0008 and overall for the SS.

Time since first diagnosis will be summarized as a continuous variable and as categorical variable. Time since first diagnosis of AS at time of enrolment in AS0008 will be taken from the AS0008 database. Time since first diagnosis of AS at time of enrolment in AS0009 will be calculated as below, where date of diagnosis will be taken from the AS0008 database:

Time since first diagnosis

$$\begin{aligned} &= \text{Date of informed consent in AS0009} \\ &\quad - \text{Date of first diagnosis in AS0008} \end{aligned} \quad (9)$$

Time since first diagnosis for each study will be categorized as: < 5 , ≥ 5 years.

Time since first symptoms of AS at time of enrolment in AS0008 will be taken from the AS0008 database. Time since first symptoms at time of enrolment in AS0009 will be calculated as:

$$\begin{aligned} & \text{Time since first symptom} \\ & = \text{Date of informed consent in AS0009} \quad (10) \\ & \quad - \text{Date of first symptom in AS0008} \end{aligned}$$

Age at first diagnosis will be taken from the AS0008 database. AS history will be listed for the ES.

The following baseline characteristics will be summarized by treatment group at the completion of AS0008 and overall for SS:

- BASDAI total score.
- BASDAI spinal pain (Question 2).
- PGADA.
- Total spinal pain (Question 1 of the TNSP questionnaire).
- BASFI.
- ASDAS-CRP.
- CRP.
- HLA-B27 (positive, negative).
- Anti-TNF therapy prior to first dose in AS0008 (yes, no). The value in the AS0008 database for past anti-TNF therapy (as collected on the eCRF) will be used for AS0009, without additional derivation.
- NSAID therapy prior to first dose to first dose in AS0008 (yes, no). The value in the AS0008 database for past NSAID therapy (as collected on the eCRF) will be used for AS0009, without additional derivation.
- Current number of NSAID therapies (0, 1, 2, ≥ 3).
- Current synthetic disease modifying anti-rheumatic drugs (DMARDs) (methotrexate [MTX], sulfasalazine, hydroxychloroquine) (yes, no).
- Current corticosteroid use (yes, no)

One summary table will be produced for AS0008 Baseline values and another for AS0009 EV values. NSAID, HLA-B27 and anti-TNF therapy prior to first dose will be based on data collected in AS0008 and will be included in the AS0008 Baseline table only.

BASDAI, BASDAI spinal pain (Q2), PGADA, total spinal pain (Q1 of the TNSP questionnaire), BASFI, ASDAS-CRP, CRP, current NSAID, current synthetic DMARDs and current corticosteroids will be included in both tables. CRP values at AS0009 EV will be taken from the Week 48 record in the AS0008 database. For the summary of AS0009 EV data, current NSAID, current synthetic DMARD and current corticosteroid therapy are defined as medications that are

ongoing at the AS0009 EV, or that started on the date of the AS0009 EV. This does not include medications that were stopped on the date of the AS0009 EV. In addition, for AS0009, current corticosteroid therapy will include oral medications only.

Baseline characteristics, including AS0008 Baseline and AS0009 EV values for the repeated variables, will be listed for the ES.

6.3 Medical history and concomitant diseases

Medical history and ongoing medical conditions collected prior to first study medication administration in AS0008 and any additional conditions collected prior to first dose of study medication in AS0009 will be summarized together. The number and percentage of subjects with any condition, and with each condition in each MedDRA SOC and PT, will be presented by treatment group at the completion of AS0008 and overall, for the SS.

Medical history and ongoing medical conditions, including the start date and end date (or ongoing if applicable), will be listed for the SS. The listing will indicate whether the condition was reported in AS0009.

A glossary of all medical history conditions including the reported term, PT and SOC will also be presented.

The number and percentage of subjects with a history of each category of extra-articular manifestations (uveitis, inflammatory bowel disease [IBD], psoriasis, peripheral arthritis, enthesitis, dactylitis) will be summarized by treatment group at completion of AS0008 and overall, for the SS, based on data collected at the AS0009 EV. The number and percentage of subjects with an occurrence of extra-articular manifestations (uveitis, IBD, psoriasis) post-EV will be summarized by treatment group at completion of AS0008 and overall, for the SS. Extra-articular assessments will be listed for the SS.

6.4 Past, prior and concomitant medications

Only medications that were ongoing at the end of AS0008 or were started during AS0009 will be reported.

Concomitant medications are medications taken at least 1 day in common with the study medication dosing period in AS0009 (as defined in [Section 3.2.2](#)). A medication is classed as concomitant if the start date is no later than the end date of study medication in AS0009 + 28 days, and the stop date is either missing or on or after the start date of study medication in AS0009. This includes medications that started prior to dosing in AS0009 and continued after.

For the purposes of the analysis, past medications are medications that started and stopped prior to dosing in AS0008. These include past TNF therapy (for subgroup analyses, MI modelling and baseline characteristics) and past NSAID therapy (for Baseline characteristics).

Missing or partial medication start and stop dates will be imputed as described in [Section 4.2.3](#). Imputations of missing data will be performed before calculation of relative study days and classification as concomitant.

The number and percentage of subjects taking concomitant medications will be summarized by ATC class, presenting Anatomical Main Group (ATC Level 1), Pharmacological Subgroup (ATC level 3), and PT, by treatment group at completion of AS0008 and overall for the SS.

All medications reported in AS0009, including flags to identify concomitant and rescue medications, and start and stop days relative to the start date of study medication in AS0008 and start and stop days relative to the start of study medication in AS0009, will be listed for the ES.

A glossary of all medications including the Anatomical Main Group (ATC Level 1), Pharmacological Subgroup (ATC level 3) PT and reported term will also be presented, based on the ES.

6.5 Prohibited medication and rescue therapy

The following medication categories will be identified:

- Rescue medications as defined below. Subjects in the category ‘Any concomitant rescue therapy in AS0009’ will be considered SS Sub-population 2 and other subjects will be considered SS Sub-population 1. Rescue medications will be identified using the flag collected in the eCRF.
- NSAIDs to identify subgroups/covariates.
- Prohibited medications.

Rescue medications and NSAIDs will be classified into subcategories for reporting purposes. The identification and classification of concomitant medications will be performed by merging an external physician-reviewed spreadsheet (which includes relevant flags for selecting medications in each category) with the data entered into the study database in order to categorize the medications correctly for the tables.

The number and percentage of subjects who receive the following categories of rescue medication will be summarized by treatment group at completion of AS0008 and overall for the SS.

- Any rescue medication in AS0009 that is classified as a concomitant medication as defined in [Section 6.4](#).
- NSAID at AS0009 EV
- No NSAID at AS0009 EV
 - No NSAID at AS0009 EV and initiate NSAID [but not Cox-2 inhibitors] in AS0009 (only the initiation of NSAIDs that are classified as concomitant medications as defined in [Section 6.4](#) will be included).
 - No NSAID at AS0009 EV and initiate Cox-2 inhibitors in AS0009 (only the initiation of Cox-2 inhibitors that are classified as concomitant medications as defined in [Section 6.4](#) will be included).
- Use of any DMARDs in AS0009 alone or in combination (includes MTX, sulfasalazine, leflunomide and hydroxychloroquine). Only concomitant medications will be included as defined in [Section 6.4](#).
- Intra-articular corticosteroid in AS0009 that is classified as concomitant as defined in [Section 6.4](#).
- Oral corticosteroid in AS0009 that is classified as concomitant as defined in [Section 6.4](#).

- Analgesics in AS0009 that are classified as concomitant as defined in [Section 6.4](#).

Rescue therapy category and medication name, start date and day relative to start of study medication in AS0008 and AS0009 will be listed for the SS.

PRN analgesic and PRN opioid analgesic use within 24 hours prior to study visits will be listed for the ES, based on the dedicated eCRF page for prohibited medications.

6.6 Concomitant medical procedures and procedure history

A listing of concomitant medical procedures and a separate listing of procedure history will be presented for the ES.

7 MEASUREMENTS OF TREATMENT COMPLIANCE

Compliance will be summarized as the number of doses received relative to the number of doses expected:

$$\frac{\text{Percent treatment compliance} = 100 * (\text{Number of doses received})}{\text{Number of doses expected}} \quad (11)$$

where the total number of expected doses is derived relative to when the subject finishes treatment. If a subject completes OLE treatment 52 doses are expected (EV and every 4th week afterwards until AS0009 Week 204). If a subject discontinues early, then the number of expected doses is based on the time of study discontinuation relative to the planned dosing visits (taking into account the permitted visit window). If the date of study discontinuation is missing the final contact date (as reported on the eCRF) will be used instead.

A summary of percent treatment compliance, both continuous and categorized as $\leq 75\%$ and $>75\%$, will be provided by treatment group at completion of AS0008 (see [Section 3.7](#)) and overall for the SS.

Treatment compliance will be listed for the SS.

A summary of the injection setting (study site/home) and person performing the injection (site personnel/subject/caregiver) will be presented by dosing visit (excluding unscheduled dosing visits) and treatment at completion of AS0008 and overall for the SS. The summary will include the total number of subjects injected at each visit and the number and percentage of subjects in each category for injection setting and person performing the injection. Percentages will be based on the number of subjects injected at each visit.

An additional summary, by treatment at completion of AS0008 and overall, will present the number and percentage of subjects in each of the following categories:

- One or more self-administrations during the study
- One or more home administrations during the study
- One or more self-administrations also performed at home during the study

Percentages will be based on the number of subjects in the SS for each treatment group or overall, as applicable.

A listing of study medication administration (including injection dates and times, kit numbers, who performed the injection, and the location of the injection) will be presented.

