6.3.1 Potential drug-induced liver injury IMP discontinuation criteria

Subjects with PDILI must be assessed to determine if IMP must be discontinued. In addition, all concomitant medications and herbal supplements that are not medically necessary should also be discontinued.

The PDILI criteria below require immediate discontinuation of IMP:

Subjects with either of the following:

- ALT or AST ≥ 5 x upper limit of normal (ULN)
- ALT or AST ≥ 3 xULN and coexisting total bilirubin ≥ 2 xULN
- Subjects with ALT or AST ≥ 3 xULN who exhibit temporally associated symptoms of hepatitis or hypersensitivity. Hepatitis symptoms include fatigue, nausea, vomiting, right upper quadrant pain or tenderness. Hypersensitivity symptoms include fever (without clear alternative cause), rash, or eosinophilia (ie, $>5\%$).

The PDILI criterion below allows for subjects to continue on IMP at the discretion of the Investigator.

- Subjects with ALT or AST ≥ 3 xULN (and ≥ 2 x Baseline) and <5 xULN, total bilirubin <2 xULN, and no eosinophilia (ie, $\leq 5\%$), with no fever, rash, or symptoms of hepatitis (eg, fatigue, nausea, vomiting, right upper quadrant pain or tenderness).

Evaluation of PDILI must be initiated as described in [Section 9.4.1](#).

If subjects are unable to comply with the applicable monitoring schedule, IMP must be discontinued immediately.

Investigators should attempt to obtain information on subjects in the case of IMP discontinuation to complete the final evaluation. Subjects with PDILI should not be withdrawn from the study until investigation and monitoring are complete. All results of these evaluations and observations, as well as the reason(s) for IMP discontinuation and subject withdrawal (if applicable), must be recorded in the source documents. The CRF must document the primary reason for IMP discontinuation.

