7.8.2 Prohibited concomitant treatments (medications and therapies)

Medications listed in [Table 7-1](#) are prohibited or restricted as follows:

Table 7-1: Prohibited or restricted medications

Drug class	Dose	Comments
Analgesics, including opioid analgesics (acetaminophen/paracetamol, etc)	Any dose	Any ad hoc use in the 24 hours prior to any study visit is prohibited. Stable doses of analgesics (including opioids) permitted.
TNF inhibitors -infliximab -adalimumab -etanercept -golimumab -certolizumab pegol	Any dose	This applies to biosimilar versions of any TNF inhibitor.
Any non-TNF biologic medications	Any dose	Any exposure history is prohibited.
All other DMARDs	Any dose	Only permitted medications as per Section 7.8.1 .

DMARD=disease-modifying antirheumatic drug; TNF=tumor necrosis factor

Subjects who take prohibited medications may be withdrawn from study treatment but followed until the SFU Visit. The decision to withdraw a subject for taking prohibited medications should be made in consultation with the Medical Monitor.

Vaccines

Administration of live, attenuated vaccines is not allowed during the conduct of the study or for 20 weeks after the last dose of IMP. Administration of non-live, inactivated vaccines is allowed during the study at the discretion of the Investigator.

Live vaccinations include, but are not limited to, the following: anthrax vaccine, intranasal influenza vaccine, measles-mumps-rubella vaccine, polio live oral vaccine, smallpox vaccine, TB Bacillus Calmette-Guérin vaccine, typhoid live oral vaccine, varicella vaccine, and yellow fever vaccine.

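### Expected doses for early leavers are counted to study discontinuation, so compliance is understated for subjects who stop study drug but stay in the study

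*SAP*

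**What the plan says.** SAP Section 7 defines percent compliance as doses received over doses expected. The general statement is that "the total number of expected doses is derived relative to when the subject finishes treatment". Two working rules follow.

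- A subject who completes open-label treatment has 52 expected doses, from the entry visit to Week 204.
- For a subject who leaves early, "then the number of expected doses is based on the time of study discontinuation relative to the planned dosing visits", allowing for the permitted visit window. There is one fallback: "If the date of study discontinuation is missing the final contact date (as reported on the eCRF) will be used instead".

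Compliance is summarised as a continuous variable and as ≤75% or >75%, and is listed, for the Safety Set.

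The protocol provides for time in the study without drug. Under Section 7.8.2, subjects who take prohibited medication "may be withdrawn from study treatment but followed until the SFU Visit". Under Section 6.3.1, some liver-injury (PDILI) criteria require study drug to stop, yet "Subjects with PDILI should not be withdrawn from the study until investigation and monitoring are complete". Withdrawal criterion 12 in Section 6.3 has subjects with new or flaring inflammatory bowel disease stop study drug and be followed until active symptoms resolve. Section 5.1 places the SFU visit 20 weeks after the last dose.

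**The concern.** The general statement and the early-leaver rule use different dates. SAP Section 5.1 itself treats them as different events, with one eCRF page for study termination and another for study medication discontinuation. A programmer will follow the early-leaver rule, because it is the operational one.

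For a subject taken off drug under the protocol but kept in the study, each planned dosing visit after the stop then enters the denominator as a dose not taken. Completers are protected, because their denominator is fixed at 52 and their off-drug weeks never count. The error can only lower compliance. It falls most heavily on subjects with few doses, and it mixes stops that the protocol directs or allows with doses that were simply missed.

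**Working it through.** **Inputs**

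- Compliance formula, 52 doses for completers, 75% cut: SAP Section 7.
- Dosing interval 28 days: SAP Section 3.2.2.
- Visit window ±7 days; SFU visit at 20 weeks (140 days) after the last dose, window −3/+7 days, so day 137 to 147: Protocol Section 8.
- Not fixed by the documents: which date is study discontinuation, and how the ±7-day window enters the count. Ranges are shown for both.

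**Step 1. The plan's own figure.** 204/4 + 1 = 52 doses, as stated.

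**Step 2. Formula.** A subject takes all *d* planned doses up to a last dose at Week 4(*d* − 1), then stops drug. Let *k* be the number of later planned dosing visits counted as expected by the study discontinuation date.

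Compliance = 100 × *d*/(*d* + *k*), with *d* + *k* capped at 52.

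It is ≤75% when *d* ≤ 0.75(*d* + *k*), that is, when *d* ≤ 3*k*.

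**Step 3. How large *k* is.** Planned doses after the last one fall on days 28, 56, 84, 112 and 140. A dose could be treated as expected when its window opens (−7 days), on its nominal day, or when its window closes (+7 days).

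- Discontinuation before day 28: *k* = 0 on the nominal and window-closing readings. On the window-opening reading, *k* = 0 only before day 28 − 7 = 21.
- Discontinuation on day 35: *k* = 1 on all three readings.
- Discontinuation dated at SFU (day 137 to 147): the day-112 dose always counts, since its window closes on day 119. The day-140 dose counts or not depending on the reading and the exact day. A day-168 dose never counts, since its window opens on day 161. So *k* = 4 or 5.

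**Step 4. Compliance of a subject who missed nothing before stopping**

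| Last dose | *d* | *k* = 1 | *k* = 4 | *k* = 5 |
|---|---|---|---|---|
| Week 8 | 3 | 75.0% | 42.9% | 37.5% |
| Week 12 | 4 | 80.0% | 50.0% | 44.4% |
| Week 36 | 10 | 90.9% | 71.4% | 66.7% |
| Week 44 | 12 | 92.3% | 75.0% | 70.6% |
| Week 48 | 13 | 92.9% | 76.5% | 72.2% |
| Week 56 | 15 | 93.8% | 78.9% | 75.0% |
| Week 60 | 16 | 94.1% | 80.0% | 76.2% |
| Week 100 | 26 | 96.3% | 86.7% | 83.9% |

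The limits *d* ≤ 3*k* are 3 doses for *k* = 1 (Week 8), 12 for *k* = 4 (Week 44) and 15 for *k* = 5 (Week 56).

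**Step 5. With the count stopped at permanent discontinuation of drug.** If that decision is recorded before the next dose falls due, *k* = 0 and every row reads 100%.

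**The case against.** The strongest reply is that study discontinuation is probably not dated at SFU. SAP Section 2.3 has early withdrawers complete the Early Termination (ET) visit and then enter the SFU period, so withdrawal comes first. SAP Section 5.1 counts a subject as a study completer at Week 208, also before SFU, and lists premature discontinuation and final contact as separate dates. Most criteria in Protocol Section 6.3 withdraw the subject from the study itself. On that reading the surplus is usually 0 or 1. This limits the size, and it stands. It does not remove the problem for subjects held in the study off drug, and the SAP never says which date applies.

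Protocol Section 7.8.2 does not settle the matter the other way: follow-up to SFU also applies to ordinary early withdrawals, so it does not show that discontinuation is recorded at SFU. PDILI retention is a clear off-drug case, but it lasts until monitoring is complete, and nothing equates that with 20 weeks.

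A second reply is that counting to study discontinuation catches real non-adherence, such as a subject who stops injecting at home for months and then withdraws. This also stands, and it rules out the date of last dose as a simple replacement: that anchor would erase every missed dose at the end of treatment and score such a subject 100%.

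A third reply is that little depends on the result. No analysis set uses the 75% cut, exposure and event rates rest on dosing dates (SAP Section 10.1), and every injection is listed. That is correct.

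**Conclusion.** The inconsistency in SAP Section 7 is real, and its effect runs in one direction. As written, the rule counts planned dosing visits after study drug was stopped as missed doses for subjects who remain in the study. The size rests on two assumptions that the documents leave open:

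- If study discontinuation is dated before the next dose falls due, there is no error.
- With one surplus dose, only subjects with at most 3 doses reach ≤75%.
- If it is dated at SFU, fully compliant subjects with at most 12 to 15 of the 52 doses are classed ≤75%; later leavers are understated but not reclassified (84–87% after 26 doses).

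A reader might infer that every fully compliant subject followed off drug lands in the ≤75% category, or that such subjects dominate it. The documents do not support either reading. The first fails for anyone beyond 15 doses even if the date is SFU. The second would need a count of affected subjects, which the documents do not give. Nor is final contact a routine anchor: it applies only when the discontinuation date is missing.

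The consequence is confined to the descriptive compliance summary and its listing. No efficacy or safety result changes.

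**What to change.** Amend the early-leaver rule in SAP Section 7 as follows.

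- Count expected doses to the earlier of the recorded decision to discontinue study medication permanently and study discontinuation. Do not count dosing visits after permanent discontinuation of drug.
- Where no separate medication discontinuation is recorded, keep study discontinuation as the anchor, so that doses missed before withdrawal still count. Do not fall back to the date of last dose.
- Define which date is study discontinuation.
- State when a dose becomes expected relative to its ±7-day window: at opening, nominal day or closing.

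The cost is a few sentences and a change to one derivation. One check is needed first. SAP Section 5.1 takes medication discontinuation and its reason from a dedicated eCRF page but mentions no date on it, and it lets the study termination page prevail where the two disagree. SAP Section 4.2.4 places the date of last administration on the study termination page. The sponsor should confirm that the decision to stop drug carries a usable date, and name its source in the SAP.
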